6.1. Demographics, Baseline Characteristics, and Disease History

6.1.1. Demographics and Baseline Characteristics

The following demographics and baseline characteristics will be summarized for the FAS: age, sex, race, ethnicity, weight, and height.

6.1.2. Baseline Disease Characteristics and Disease History

The following baseline disease characteristics may be summarized for all or applicable participants in the FAS: primary diagnosis, time since diagnosis, time since metastatic disease or diagnosis of locally advanced inoperable cancer, stage at initial diagnosis, disease histology, histological grade, P16/HPV (for participants with SCCHN)/PD-L1 status, MSI-h/dMMR status, mutation status (listing), and ECOG performance status.

6.1.3. **Prior Therapy**

The number of participants receiving any prior therapy and the number of prior systemic cancer therapy regimens will be summarized for all participants in the FAS. The regimen name, component drugs, start and stop dates, purpose of the regimen, best response, reason for discontinuation, and date of relapse/progression will be listed.

For participants who received prior radiation, the body site, start and stop dates, and total dose will be listed.

For participants who had prior surgery or surgical procedure for the malignancies under study, the date and description of the surgery/procedure will be listed.

6.1.4. Medical History

For participants in the FAS who experienced past and/or concomitant medical conditions, the medical history condition/event, start and end dates, and whether the condition was ongoing or intermittent will be listed.

6.2. Disposition of Participant

The number and percentage of participants who were enrolled, who were treated, who were ongoing with study treatment, who discontinued study treatment with a primary reason for discontinuation, who were still in the study, who completed the study, and who withdrew from the study with a primary reason for withdrawal will be summarized for the FAS. The number of participants enrolled by country and/or site will also be provided by treatment group.

6.3. **Protocol Deviations**

Protocol deviations recorded may be summarized and listed.

6.4. Exposure

For participants in the safety population, exposure to INCB001158 and pembrolizumab will be summarized descriptively as follows:

- Exposure to INCB001158
 - Total actual dose (mg): total actual dose taken of INCB001158.
 - Duration of treatment with INCB001158 (days): date of last dose of INCB001158 – date of first dose of INCB001158 + 1.
 - Average daily dose of INCB001158 (mg/day): total actual INCB001158 dose taken (mg) / duration of treatment with INCB001158 with nonzero dosing (days).
- Exposure to pembrolizumab
 - Number of cycles: number of cycles with a nonzero dose of pembrolizumab.
 - **Total number of infusions:** total number of infusions per participant with a nonzero dose of pembrolizumab.
 - **Total dose administered (mg):** sum of the cumulative dose of pembrolizumab that has been administered to the participant.

For an infusion *i*, let C_i be the concentration (mg/mL) of pembrolizumab and V_i be the total volume administered (in mL) reported on the pembrolizumab dosing eCRF; let *N* be the total number of infusions:

total dose administered (mg) = $\sum_{i=1}^{N} C_i \times V_i$.

- Average dose (mg): total dose administered (mg) / the total number of infusions.

6.5. Study Drug Compliance

For participants in the safety population, overall compliance (%) for INCB001158 will be calculated as follows:

compliance (%) = $100 \times [\text{total dose actually taken}] / [\text{total prescribed dose}].$

The total prescribed dose is defined as the sum of the doses prescribed by the investigator accounting for dose modifications.

The total actual dose taken will be calculated based on information entered on the Drug Accountability eCRF. If there are dispensed drugs that have not been returned yet, the actual dose taken starting from the dispense date of the unreturned drugs will be imputed by the dose taken as reported on the Dosing eCRF.

6.6. Prior and Concomitant Medication

Prior medications and concomitant medications will be coded using the WHO Drug Dictionary. The number and percentage of participants in the FAS for each prior and concomitant medication will be summarized by WHO drug class and WHO drug PT.

7. EFFICACY

Appendix A provides a list of data displays. Sample data displays are included in a separate document.

7.1. General Considerations

This study had no primary efficacy endpoint. The secondary efficacy endpoints include ORR, BOR, DOR, and PFS by investigator assessment based on RECIST v1.1.

7.2. Efficacy Hypotheses

Each Simon 2-stage design (Simon 1989) will test the null hypothesis that the true ORR is less than or equal to the clinically insignificant response rate p_0 % against the alternative hypothesis that the true ORR is equal to or greater than the target rate of p_1 %. For each Simon 2-stage design, the value for p_0 is determined by a historical response rate (refer to Protocol Section 15.2).

7.3. Analysis of the Efficacy Parameters

7.3.1. Response Criteria

Overall disease status will be categorized using RECIST v1.1 (Eisenhauer et al 2009) based on investigator assessment. Participants will have their overall response evaluated as CR, PR, SD, non-CR/non-PD (only for participants with nonmeasureable disease alone at baseline), PD, or NE at each postbaseline radiologic assessment based on changes in target lesions, nontarget lesions, and appearance of new lesions.

7.3.2. Unconfirmed and Confirmed Best Overall Response

In general, under RECIST v1.1, the unconfirmed best overall response is the best response recorded postbaseline prior to and including the first PD, in the order of CR, PR, SD (non-CR/non-PD), PD, and NE. The best overall response will be determined from response assessments prior to or on the same day as new anticancer therapy. If any alternative cancer therapy is taken while on study, any subsequent assessments will be excluded from the best overall response determination.

In the case of SD (non-CR/non-PD), measurements must meet the SD (non-CR/non-PD) criteria at least once after the date of first dose at a minimum interval of 8 weeks. Participants that fail to meet this criterion will have best overall response of PD if the next available assessment indicates PD or NE if there is no additional assessment available.

The participant's confirmed best overall response assessment will depend on the achievement of both measurement and confirmation criteria in Table 3.

First Timepoint Response	Second Timepoint Response	Confirmed Response
CR	CR	CR or SD or NE ^a
CR	PR ^b	SD or NE ^c
CR	PR ^a	SD or NE ^a
CR	Non-CR/Non-PD ^d	Non-CR/Non-PD ^a or NE
CR	PD	SD or NE ^a or Non-CR/Non-PD ^a
CR	NE	SD or NE ^a or Non-CR/Non-PD ^a
CR	No further evaluation	SD or NE ^a or Non-CR/Non-PD ^a
PR	CR	PR or SD or NE ^e
PR	PR	PR or SD or NE ^a
PR	SD	SD or NE ^a
PR	NE	SD or NE ^a
PR	PD	SD or NE ^a
PR	No further evaluation	SD or NE ^a
SD	CR	SD or NE ^a
SD	PR	SD or NE ^a
SD	SD	SD or NE ^a
SD	PD	SD or NE ^a
SD	NE	SD or NE ^a
SD	No further evaluation	SD or NE ^a
Non-CR/Non-PD ^a	CR	Non-CR/Non-PD ^a or NE
Non-CR/Non-PD ^a	Non-CR/Non-PD ^a	Non-CR/Non-PD ^a or NE
Non-CR/Non-PD ^a	PD	Non-CR/Non-PD ^a or NE
Non-CR/Non-PD ^a	NE	Non-CR/Non-PD ^a or NE
Non-CR/Non-PD ^a	No further evaluation	Non-CR/Non-PD ^a or NE
PD	No further evaluation	PD
NE	CR	NE
NE	PR	NE
NE	SD	NE
NE	Non-CR/Non-PD ^a	NE
NE	PD	NE
NE	NE	NE
NE	No further evaluation	NE

 Table 3:
 Confirmed Response Based on Subsequent Assessments

Note: A confirmed response of SD can only be made after the participant is on-study for a minimum of 8 weeks according to study protocol or SAP. If the participant is on-study less than 8 weeks, any tumor assessment indicating stable disease before this time period will have a confirmed response of NE. NE is not required to be confirmed according to the table.

Note: Subsequent documentation of CR may provide confirmation of a previously identified CR for participants where the second integrated response was NE. Subsequent documentation of PR may provide confirmation of a previously identified PR for participants where the second integrated response was NE or SD. If the third tumor assessment confirms the CR (or PR) then the confirmed response will be CR (or PR). Only 1 intervening NE is allowed between CRs/PRs. For example: CR NE CR = CR; PR NE PR/CR = PR. Additionally, 1 SD ($\geq 25\%$ reduction in target lesions comparing with baseline) is allowed between PRs (eg, PR SD PR/CR = PR). Note: in the following scenario, PR SD NE PR, the second PR is not a confirmed PR.

- ^a Confirmed response is CR if gap (4 weeks) is met. Otherwise, confirmed response is SD if at least 8 weeks on study, or NE if within 8 weeks on study.
- ^a Special case programming: assign PR or SD following CR as PD in confirmed response.
- ^a Confirmed response will be SD if the first tumor assessment is at least 8 weeks on-study. Otherwise, the confirmed response will be NE.
- ^a Non-CR/Non-PD applies to participants with nonmeasurable disease at baseline. A confirmed response of Non-CR/Non-PD can only be made after the participant is on-study for a minimum of 8 weeks according to study protocol or SAP. If the participant is on-study less than 8 weeks, any tumor assessment indicating stable disease before this time period will have a confirmed response of NE.

^a Confirmed response is PR if gap (4 weeks) is met. Otherwise, confirmed response is SD if at least 8 weeks/days on study, or NE if within 8 weeks on study.

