**Study Schedule/Procedures**

Patients will have regularly scheduled study visits at the clinical site on Day 1 of each cycle.

Additional study visits may be required during some cycles to monitor for safety, efficacy, or for PK/ [REDACTED] evaluations. Study visits are as follows:

**Screening:** Up to 21 days before enrollment. Screening will begin at the time that the Patient signs the informed consent and will continue until the date that the Patient is enrolled in the study (Cycle 1 Day 1).

Part 1a **Cycle 1:** Day 1, Day 2, Day 8, Day 15, and Day 22 ( $\pm$  2 days); **Cycle 2:** Day 1 and Day 8 ( $\pm$  5 days).

Part 2 **Cycle 1:** Day 1, Day 8, Day 15, and Day 22 ( $\pm$  2 days).

Parts 1b, 1c, and 3 **Cycle 1:** Day 1, Day 8, and Day 15 ( $\pm$  2 days).

**All other treatment cycles:** Day 1 ( $\pm$  5 days).

**Part 1a and 2 Efficacy assessments:** Every 8 weeks ( $\pm$  7 days).

**Part 1b, 1c, and 3 Efficacy assessments:** Every 9 weeks ( $\pm$  7 days).

**End of treatment:** The End of Treatment (EOT) visit must occur within 28 days of study treatment discontinuation and prior to initiation of any new anti-cancer therapy/regimen.

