**11.3 Other Schedules and Procedures**

For Study Parts 1a and 2, radiographic evaluation of tumor burden (e.g., diagnostic CT/MRI) will occur at Screening and approximately every 8 weeks after study initiation, or more frequently as clinically indicated.

For Study Parts 1b and 3, radiographic evaluation of tumor burden (e.g., diagnostic CT/MRI) will occur at Screening and approximately every 9 weeks after study initiation, or more frequently as clinically indicated.

Optional tumor biopsies may be obtained at variable time points as advised by the Investigator and Medical Monitor and agreed by the patient.

During study treatment, urine pregnancy tests will be performed locally as medically indicated, or per country-specific requirement. If a urine pregnancy test is positive, then the results should be confirmed with a serum pregnancy test.

If the serum pregnancy test is negative after a urine test was positive, then the investigator will assess the potential benefit/risk to the subject and determine whether it is in the subject's best interest to resume study treatment and continue participation in the study.

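### The SAP's 8-week minimum for stable disease ignores the 7-day scan window in the monotherapy parts, so an on-schedule SD scan on days 49 to 55 does not count and best overall response can become PD or NE

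*SAP*

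**What the plan says.** **Scan schedule.** The protocol synopsis (Study Schedule/Procedures) sets efficacy scans every 8 weeks in Parts 1a and 2 and every 9 weeks in Parts 1b, 1c and 3, each with a window of 7 days either way. Protocol 11.3 gives the anchor for the monotherapy parts: imaging "will occur at Screening and approximately every 8 weeks after study initiation".

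**SD minimum in the text.** SAP 7.3.2 requires that "measurements must meet the SD (non-CR/non-PD) criteria at least once after the date of first dose at a minimum interval of 8 weeks". A patient who fails this "will have best overall response of PD if the next available assessment indicates PD or NE if there is no additional assessment available".

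**SD minimum in Table 3 (confirmed response).** A note, limited to patients with under 8 weeks on study, says that "any tumor assessment indicating stable disease before this time period will have a confirmed response of NE". One footnote instead tests whether the first tumor assessment itself was at least 8 weeks on study. For the sequence SD then PD, the table gives SD or NE. It gives the same pair of outcomes for a PR followed by PD or by no further evaluation.

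**Protocol minimum.** Table C in Attachment 4 refers to a minimum SD duration but gives no number. The 8 weeks is the SAP's own figure.

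**The concern.** The SAP minimum equals the nominal date of the first monotherapy scan. A site that scans a few days early, within the window the protocol allows, produces an SD reading that the SAP will not credit. The nominal date is also the Cycle 3 Day 1 visit (2 cycles x 28 days = 56 days), so in elapsed days a scan done one day ahead of that visit already falls short.

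BOR is a listed secondary endpoint, and both confirmed and unconfirmed BOR are to be tabulated for Parts 1a and 2. The Part 2 Simon designs use a background ORR of 2% and a target of 15%. Even at the target, about 85% of patients (100% - 15%) are non-responders, so the split among SD, PD and NE is most of what a monotherapy BOR table will show. That split should not depend on where in an allowed window the scan was booked.

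**Working it through.** The 8-week minimum is a stated rule with no derivation, so there is no plan figure to reproduce. The check is calendar arithmetic.

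**Inputs**
- SD minimum: 8 weeks = 56 days from first dose (SAP 7.3.2).
- Monotherapy scans: 8 weeks +/- 7 days. Combination scans: 9 weeks +/- 7 days (Protocol synopsis).
- Anchor: study initiation, taken as Cycle 1 Day 1, which SAP 4.1.5 makes the day of first dose.
- Study day = elapsed days + 1 (SAP 4.1.2).

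**First scan, Parts 1a and 2**
- Window: 56 - 7 = 49 to 56 + 7 = 63, which is 63 - 49 + 1 = 15 allowed days.
- Elapsed days below 56: 49 to 55, so 7/15 = 47% of window days fail.
- In SAP study days (elapsed + 1 < 56): elapsed days 49 to 54, so 6/15 = 40% fail.
- A scan at the nominal 56 elapsed days or later passes under either count.

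**First scan, Parts 1b, 1c and 3**
- Window: 63 - 7 = 56 to 63 + 7 = 70, also 15 days. None is below 56, so 0/15 fail.

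**What happens after an early SD (days 49 to 55)**

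The second monotherapy scan is due at 112 +/- 7 = days 105 to 119, well past the minimum.

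| Next assessment | Unconfirmed BOR (text) | Confirmed response (Table 3) |
|---|---|---|
| SD | SD | SD |
| CR or PR | CR or PR | depends on later confirmation |
| PD | PD | SD or NE, never PD |
| None | NE | SD or NE |

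In the last two rows Table 3 does not settle the result. Under the note that tests time on study, a day-50 SD in a patient still on study after week 8 may stay SD. Under the footnote that tests the first scan date, it becomes NE. Two programmers could code the same patient differently.

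**Early PR.** A PR on day 50 followed by PD, or by nothing, is not confirmed. Table 3 sends it to SD or NE on the same 8-week test, so it too can become NE in confirmed BOR.

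**Endpoints not touched.** ORR counts only CR and PR (SAP 7.3.3), and an unconfirmed PR that falls to SD or to NE is a non-responder in confirmed ORR either way. The Simon rules use responses only, DOR includes responders only, and PFS uses time-point assessments and deaths rather than BOR.

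**Patient-level illustration.** The documents give neither input, so both are assumptions. If 10% to 47% of first scans fall early, and 30% to 70% of those patients have no later SD or response, the share of first-scan SD patients recoded runs from 0.10 x 0.30 = 3% to 0.467 x 0.70 = 33%. A middle case is 0.25 x 0.50 = 12.5%.

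**After the fix.** With 49 days for Parts 1a and 2, 0/15 window days fail under either day count. With 56 days for Parts 1b, 1c and 3, the result stays 0/15.

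**The case against.** The case for leaving the rule alone has several sound parts.

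- **A fixed SD minimum is legitimate.** The protocol refers to one without a number and the SAP supplies it. Nothing in the documents obliges the SAP to subtract the visit window.
- **Most early SD patients may be rescued.** The criterion has to be met only once. Protocol 11.4 asks for a scan at end of treatment unless the patient stopped for objective progression, 11.5.2 continues scans for those who stop without progression, and 11.3 allows more frequent scans. These narrow the NE route in particular.
- **The consequence is small.** One descriptive secondary endpoint is affected, in an open-label study whose analyses are all exploratory (SAP 3.2). Time-point responses are listed (Listing 2.6.3), so the early SD stays visible.

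All of this stands, and it limits the point without removing it. A patient scanned early, stable, and progressing at the next scan still loses SD because of the booking date.

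A reader might also infer stronger claims, which the documents do not support:

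- *Every in-window SD is recoded.* No. Only an early SD with no later qualifying scan is at risk.
- *About half of monotherapy patients are affected.* No. The 47% is a share of calendar days, and nothing shows that scan dates are evenly spread.
- *The treatment groups have different SD rules.* No. One 8-week rule applies to all parts; the scan schedules differ.
- *The comparison with the combination is biased.* No such comparison of BOR is planned. The study is nonrandomized, eligibility differs by part, and response tables are separate, with Part 1c shown alongside Part 3.

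**Conclusion.** The point holds in limited form. The SD minimum in SAP 7.3.2 is later than the earliest compliant first scan in Parts 1a and 2, by up to 7 days. SD on 7 of 15 allowed days (6 of 15 as study days) is not credited at that scan, against 0 of 15 in Parts 1b, 1c and 3. Where no later scan shows SD or a response, unconfirmed BOR can become PD or NE and confirmed BOR can become NE. Some unconfirmed PRs meet the same test.

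The effect is confined to the SD/PD/NE split of BOR in the monotherapy parts. How many patients it reaches cannot be derived from the documents; the 3% to 33% range rests wholly on assumed inputs. The calendar result assumes that study initiation means the day of first dose and that 8 weeks means 56 days. The disagreement between the 7.3.2 text and Table 3, and within the Table 3 notes, needs settling whatever minimum is kept.

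**What to change.** In SAP 7.3.2 and the Table 3 notes:

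1. Define the SD minimum as the scheduled first scan minus its window: 49 days after first dose for Parts 1a and 2, and 56 days for Parts 1b, 1c and 3.
2. State whether the minimum is counted in elapsed days or SAP study days.
3. State whether the test applies to the date of the scan or to time on study, and use that one test in the text, the notes and the footnotes.
4. Say whether early SD followed by PD gives PD or NE, and make the text and Table 3 agree.
5. Apply the same minimum to unconfirmed PR and CR that fall back to SD or NE.

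The cost is a few lines of SAP text and one programming constant per schedule. There are two downsides: SD can be credited up to one week earlier in the monotherapy parts, and the numeric minimum then differs by scan schedule, which a table footnote should say.

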7.3.3. Objective Response Rate

A participant is considered an objective responder if they have a best overall response of CR or PR before first PD and start of any subsequent anticancer therapy.

The ORR based on both unconfirmed and confirmed best overall responses will be estimated with 95% CIs. Confidence intervals will be calculated based on the exact method for binomial distributions.

7.3.4. Duration of Response

For objective responders, the DOR is the time from the first overall response contributing to an objective response to the earlier of the participant's death or first overall response of PD as assessed by RECIST v1.1 occurring after the first overall response contributing to the objective response. Partial death dates will be handled using the rules described in Section 4.1.4. Censoring of DOR will follow the same algorithm as the censoring of PFS (see Section 7.3.6).

Kaplan-Meier curves for DOR based on both unconfirmed and confirmed responses will be presented by treatment group. The Kaplan-Meier estimate of median DOR will be presented with its 95% CI. The 95% CI will be calculated using the generalization of Brookmeyer and Crowley's method (1982) with log-log transformation (Klein and Moeschberger 1997).

Duration of response analyses will only include responders, and any Kaplan-Meier analyses will only be provided if appropriate. For example, if there are a very small number of responders, Kaplan-Meier analysis will not be provided.

7.3.5. Largest Percentage Reduction in Sum of Diameters of Target Lesions

For each participant in the FAS with target lesions at baseline, target lesion sizes will be measured by the sum of the diameters. The best percent change from baseline, defined as the largest decrease in target lesion size for each participant, will be summarized descriptively, and a waterfall plot of the best percent change will be generated. Note that for participants who only have increases in target lesion sizes from baseline, the smallest increase will be considered as the best change from baseline.

Per RECIST v1.1 criteria, target lesions considered "too small to measure" will be assigned a default value of 5 mm for purposes of this analysis. Likewise, target lesions identified as "not present" at postbaseline assessments will be assigned 0 mm for this analysis. In the event a target lesion is unaccounted for in a particular postbaseline timepoint (ie, assessment missing or NE), then the overall sum of diameters for target lesions will not be evaluable for that postbaseline timepoint.

7.3.6. **Progression-Free Survival**

Progression-free survival is defined as the length of time between the date of first dose and the earlier of death or PD as assessed by RECIST v1.1 per investigator assessment. Partial death dates will be handled using the rules described in Section 4.1.4. Censoring for PFS will follow the algorithm outlined in Table 4, which is based on FDA guidance (FDA 2015, FDA 2018).

Situation	Outcome	Date of Progression or Censoring
No baseline tumor assessments	Censored	Day 1
No valid postbaseline response assessments	Censored	Day 1
Progression documented between scheduled response assessments	Progressed	Date of first overall response of PD
No progression	Censored	Date of last valid radiologic assessment (not NE and not missing)
Study discontinuation for undocumented progression	Censored	Date of last valid radiologic assessment (not NE and not missing)
Study discontinuation for toxicity or other reason	Censored	Date of last valid radiologic assessment (not NE and not missing)
New anticancer treatment started	Censored	Date of last valid radiologic assessment (not NE and not missing) on/before starting a new anticancer treatment
Death before first progressive response assessment	Progressed	Date of death
Death between adequate response assessments	Progressed	Date of death
Death or progression after 2 or more missed assessments	Censored	Date of last valid radiologic assessment (not NE and not missing)

Table 4:Evaluation and Censoring of Progression-Free Survival

Kaplan-Meier curves for PFS will be presented by treatment groups. The Kaplan-Meier estimate of median PFS will be presented with its 95% CI. The 95% CI will be calculated using the generalization of Brookmeyer and Crowley's method (1982) with log-log transformation (Klein and Moeschberger 1997).

